## **10.5 Sample Size**

Since this is an exploratory pilot study and we are not formally testing a specific research hypothesis, the sample size for each arm has been chosen based on practical considerations and estimated feasibility. However, for the primary analysis (arm 1), we consider a predictive model with a true AUC of at least 0.7 promising for predicting initial objective response. With 20 patients and assuming that 59% of patients have an objective response to treatment, a predictive model with a true AUC of at least 0.7 will have a margin of error of 0.14 so that the empirically determined AUC can range from 0.56 to 1.

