## PROTOCOL SYNOPSIS

TITLE	Early therapeutic monitoring of response to therapy with serial ultrasound in metastatic RCC
STUDY PHASE	Pilot
INDICATION	Metastatic Renal Cell Carcinoma (mRCC)
INVESTIGATIONAL PRODUCT OR PROCEDURE	Study of power Doppler ultrasound for early detection of therapeutic response after initiating therapy with: arm 1: tyrosine kinase (TKI) inhibitor plus immune checkpoint inhibitor (ICI) arm 2: non-ICI therapy (e.g., TKI monotherapy, combination of TKI with other kinase inhibitor, localized tumor therapy such as radiation, chemo- or radioembolization)
PRIMARY OBJECTIVE(S)	To assess whether changes in quantitative tumor perfusion parameters after 3 weeks of treatment, as measured by LEAD ultrasound, can predict initial objective response, defined by current standard-of-care, to therapy at 12 weeks after start of treatment
SECONDARY OBJECTIVE(S)	To evaluate if there is an optimal ultrasound imaging modality (power Doppler or LEAD ultrasound) or optimal time point to predict initial objective response, to assess the correlation of tumor perfusion parameters with change in overall tumor burden, change in diameter on a per-lesion basis and with 12-month progression-free survival (PFS).
STUDY PROCEDURE SUMMARY	power Doppler and LEAD ultrasound of subjects taking targeted therapy medication, measured at treatment 'baseline', 3-4 weeks, and 6-8 weeks after initiating treatment
SAMPLE SIZE	arm 1: 20 subjects arm 2: up to 10 subjects
STATISTICAL CONSIDERATIONS	We will evaluate the predictive ability of each model using area under the curve (AUC). For this pilot study, assuming that 59% of patients in arm 1 have an objective response to treatment, a predictive model with a true AUC of 0.7 will have a margin of error of 0.14 so that the estimated AUC can range from 0.56 to 0.84.

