### **10.3 Primary Analysis**

#### **10.3.1 Analysis Population**

The population for primary analysis consists of all study participants who have completed the LEAD ultrasound exams at treatment 'baseline' and after 3 weeks of treatment, who received at least 4 weeks of TKI and at least one dose of ICI therapy, and for whom initial response can be evaluated per RECIST v1.1. If fewer than 20 of the 20 initially enrolled patients in arm 1 fulfill these criteria, additional patient may be enrolled

at the discretion of the Protocol Directors to have a complete dataset from 20 patients in arm 1 for primary analysis.

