### 10.3.2 Analysis Plan

To address our primary objective, we will conduct a Least absolute shrinkage and selection operator (Lasso) regression as our primary analysis. Specifically, our outcome, initial objective response, will be regressed on the change in each of the LEAD ultrasound tumor perfusion parameters after 3 weeks of treatment and relevant demographic and clinical characteristics. The measurement of LEAD ultrasound tumor perfusion parameters and the definition of their change are described in more detail below. We will not use selection techniques to choose variables. Rather, we will include all factors in our model jointly. We will evaluate the predictive ability of our model using area under the curve (AUC) and calculate a 95% confidence interval for the AUC. Since our sample size is too small to allow for separate training and testing datasets, we will utilize cross-validation techniques for evaluating predictive performance.

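### The stated AUC margin of error of 0.14 does not follow from its inputs: 20 patients, 59% responders and a true AUC of 0.7 give a 95% margin of about 0.23, and the interval includes 0.5

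*Protocol*

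**What the plan says.** Section 10.5 first says that the size of each arm was set by practicality and feasibility, with no formal hypothesis test. It then makes a precision claim for the primary analysis. "With 20 patients and assuming that 59% of patients have an objective response to treatment", it says, "a predictive model with a true AUC of at least 0.7 will have a margin of error of 0.14", and it concludes that "the empirically determined AUC can range from 0.56 to 1". The Synopsis makes the same claim for a true AUC of exactly 0.7, with the same 0.14, but concludes that "the estimated AUC can range from 0.56 to 0.84".

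Neither place gives a confidence level or a formula. The only level the protocol attaches to the AUC is in section 10.3.2, where the analysts are to "calculate a 95% confidence interval for the AUC". Section 10.3.1 allows additional patients to be enrolled "to have a complete dataset from 20 patients in arm 1 for primary analysis", so 20 is the evaluable number. Section 10.7 makes an AUC of at least 0.7 the minimum for designing a follow-up study.

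**The concern.** An AUC estimated from about 12 responders and 8 non-responders is very imprecise, and a margin of 0.14 looks too small for it. Because the figure appears in both the sample size section and the Synopsis, it tells readers how much the pilot can show.

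The lower limit is what matters most. At 0.56 it lies above 0.5, so a reader will infer that a model reaching the protocol's threshold of 0.7 could be told apart from one with no predictive value. If the true margin is wide enough to take in 0.5, that inference fails, and a result that meets the section 10.7 threshold would be read with more confidence than 20 patients support. The two upper limits, 0.84 and 1, also need to be reconciled.

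**Working it through.** **Inputs**

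- Evaluable arm 1 patients: 20 (sections 10.3.1 and 10.5). No reduction for attrition is applied.
- Responders: 59% (section 10.5), so 0.59 × 20 = 11.8 responders and 8.2 non-responders, about 12 and 8.
- True AUC: A = 0.7. Section 10.5 says at least 0.7, but its lower limit is 0.70 − 0.14 = 0.56, so 0.7 is the value used.
- Confidence level: 95% two-sided, taken from section 10.3.2.

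**The plan's figure.** The stated limits are simply 0.70 − 0.14 = 0.56 and, in the Synopsis, 0.70 + 0.14 = 0.84. The question is whether 0.14 follows from the inputs.

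**Standard error (Hanley-McNeil).** With m responders and n non-responders,

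SE² = [A(1 − A) + (m − 1)(Q₁ − A²) + (n − 1)(Q₂ − A²)] / (mn), where Q₁ = A/(2 − A) and Q₂ = 2A²/(1 + A).

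- Q₁ = 0.7/1.3 = 0.5385, so Q₁ − A² = 0.0485
- Q₂ = 0.98/1.7 = 0.5765, so Q₂ − A² = 0.0865
- m = 12, n = 8: SE² = (0.21 + 11 × 0.0485 + 7 × 0.0865)/96 = 0.0140, so SE = 0.1185
- m = 11.8, n = 8.2: SE = 0.1184

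**95% margin.** 1.96 × 0.1184 = 0.232. The interval is 0.70 ± 0.23, or 0.47 to 0.93, and it includes 0.5.

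**Other confidence levels at A = 0.7**

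| Level | Margin | Lower limit |
|---|---|---|
| One SE (68%) | 0.118 | 0.58 |
| Two-sided 75% | 0.136 | 0.56 |
| Two-sided 80% | 0.152 | 0.55 |
| Two-sided 90% or one-sided 95% | 0.195 | 0.505 |
| Two-sided 95% | 0.232 | 0.47 |

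No conventional level gives 0.14. The level it implies is 2Φ(0.14/0.1184) − 1 = 0.763, about 76%.

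**Sensitivity to method**

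- Splits of 11/9 and 10/10 give 95% margins of 0.232 and 0.234.
- The Obuchowski binormal variance gives 0.238.
- An interval built on the logit scale runs from 0.44 to 0.88.
- A binormal simulation (12/8, 100,000 runs, true AUC 0.7) gives an SD of 0.121 and a central 95% range of 0.45 to 0.92. Only 75% of the estimates fall between 0.56 and 0.84, and 13% fall below 0.56.

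**What would give 0.14**

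- At 95% and A = 0.7, about 54 patients are needed (about 50 if 0.145 is rounded down to 0.14).
- With 20 patients at 95%, the true AUC would have to be about 0.90, where the margin is 0.139. That does not fit a lower limit of 0.56.
- One standard error under an AUC of 0.5 is √[21/(12 × 96)] = 0.135. This is the nearest simple match, but it is neither a 95% margin nor evaluated at 0.7.

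**The case against.** The strongest objection is that the margin sentence states no confidence level. The 95% comes from section 10.3.2, which concerns the interval to be calculated from the data. That is an inference, but the natural one, and it does not decide the matter, since no conventional level gives 0.14 at an AUC of 0.7. At two-sided 90% the lower limit would be about 0.505, just above 0.5 but still not 0.56.

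Second, the sample size is openly based on feasibility, the section 10.7 rule uses the point estimate with no margin, and the protocol already plans a larger cohort to narrow the margin. All of this is true. The error did not set the sample size, and correcting it changes no decision rule. What remains is a wrong figure that describes how far the pilot's result can be trusted.

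Third, it is too strong to say without qualification that the trial cannot separate a promising model from chance. At a true AUC of 0.8 the 95% margin is 0.195, giving about 0.60 to 1.0, which excludes 0.5. The statement applies at or near 0.7 with a 95% interval.

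Fourth, the upper limits of 0.84 and 1 each follow from the local wording, exactly 0.7 in one place and at least 0.7 in the other. That is a mismatch of wording, not a second arithmetic error. Reading the value as at least 0.7 explains the limit of 1 but leaves 0.56 unsupported.

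**Conclusion.** The point holds. On the protocol's own inputs the 95% margin at an AUC of 0.7 is about 0.23 (0.232 by Hanley-McNeil, 0.238 by the binormal formula). The stated 0.14 is too small by (0.232 − 0.14)/0.232, about 40%. The expected lower limit is 0.47, not 0.56, so the interval includes 0.5.

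This rests on 20 evaluable patients, about 59% responders, a true AUC of 0.7 and a two-sided 95% level; the exact split hardly matters. The formulas also treat the score as fixed in advance. The protocol plans a cross-validated Lasso fitted in the same 20 patients, whose AUC would probably vary more, so 0.23 is if anything optimistic; no size is put on that extra variation here. The choice of 20 patients is not in question, only the precision claimed for it.

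**What to change.** Replace the precision sentence in section 10.5 and in the Synopsis with the same text, for example:

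> With 20 evaluable arm 1 patients, 59% of them responders, a model whose true AUC is 0.7 has a 95% margin of error of about 0.23 (Hanley-McNeil), i.e. 0.47 to 0.93, before any added variability from cross-validation. At this AUC the interval is not expected to exclude 0.5.

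Use one AUC value and one range in both places. If a level other than 95% was intended, name it and recompute the margin at that level.

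The cost is a wording change in two places and a less favourable stated precision. Enrolment, study procedures, the analysis and the section 10.7 threshold stay as they are.

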## **10.6 Accrual estimates**

We estimate that 15 patients yearly are eligible for arm 1 and approximately 10 patients for arm 2. By experience from previous similar imaging studies, patients are motivated to participate in such studies, especially when they do not require extra study visits. However, taking into account attrition, we conservatively estimate that it will take 2 years to accrue 20 patients in arm 1 and up to 10 patients in arm 2 who complete all ultrasound exams, receive treatment over the minimum period, and will have an evaluable response per RECIST.

## **10.7 Criteria for future studies**

An AUC of at least 0.7 will be the minimum needed to design a follow-up study and the predictive model that yields the best AUC will be selected for future studies. If different predictive models give equivalent AUCs, we will consider additional analyses (for example, random forests or Classification and Regression Tree [CART]) to evaluate these models to determine if a specific model can be selected for further studies.

If any predictive model from this pilot study has an AUC of at least 0.7, the next step will be to conduct a larger follow-up study in an independent cohort to validate the predictive model and determine its AUC with a smaller margin of error. The sample size and operating characteristics of the follow-up study will be determined based on findings from this pilot study and other data available at the time of designing the follow-up study. If the larger follow-up study is also deemed a success (AUC at least 0.7), to determine if tumor perfusion measurements by ultrasound are suitable for implementation, an adequately powered randomized clinical trial will be required to

Early Therapeutic Monitoring of Response to Therapy with Serial Ultrasound in Metastatic Renal Cell Carcinoma

test if an early therapy switch based on ultrasound imaging improves outcomes, compared to current standard of care.

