## 10.4 Secondary Analysis

### 10.4.1 Analysis Population

All patients who have completed at least one LEAD and Doppler ultrasound exam at any time point. For correlation analyses, patients are included for each analysis based on availability of data points for specific analyses. If fewer than 20 patients in arm 1 and 10 patients in arm 2 fulfill these criteria for any secondary analysis, additional patient may be enrolled at the discretion of the Protocol Directors to have a complete dataset from 20 and 10 patients for this analysis, respectively.

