### 10.4.2 Analysis Plan

To address our secondary objective, i.e., evaluating if there is an optimal ultrasound modality to predict initial objective response in arm 1, we will utilize the same analysis approach as outlined above for the primary analysis. Here, we will use change in tumor perfusion parameters at **6 weeks** as our independent variables and conduct two regression analyses: (1) using power Doppler measurements and (2) using LEAD ultrasound measurements. AUCs between the two models will be compared using the nonparametric approach of DeLong for correlated AUC curves. In addition, we will compare AUCs between these models to the predictive model for the primary analysis.

To assess if there is an optimal time point for predicting initial objective response in arm 1, we will conduct Lasso regression models using tumor perfusion parameters for each time point (treatment 'baseline', 3 weeks, 6 weeks) separately for each imaging modality using a similar approach as outlined above. Given the exploratory nature of these analyses, we will not adjust for multiple testing.

For each arm, we will conduct correlation analysis for change in perfusion parameters at 3 and 6 weeks and initial relative change in tumor burden (overall and per-lesion), initial overall response, best overall response, and PFS until 12 months after initiating treatment by calculating either the Pearson r or Spearman rank correlation, as appropriate. PFS is estimated using the Kaplan-Meier method and the Kaplan-Meier curves will be presented.

Selection of lesions for ultrasound exams:

The up to 5 lesions that were selected for ultrasound studies for the primary analysis are re-assessed 6 weeks (+/- 15 days) after start of treatment and each lesion is assessed with both LEAD and power Doppler ultrasound at all 3 time points (treatment 'baseline', 3 weeks, and 6 weeks after initiating treatment).

Quantification and change of tumor perfusion parameters: defined in the same way as for the primary analysis for both power Doppler and LEAD ultrasound.

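### Section 10.7 takes forward the best of at least nine AUCs from largely the same 20 patients and asks for no figure corrected for that choice; the bias is real, the harm limited, the repair cheap

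*Protocol*

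**What the plan says.** **Models.** Section 10.3.2 of the protocol fits a Lasso model for initial objective response to the 3-week change in LEAD parameters. Because 20 patients cannot be split into training and test sets, "we will utilize cross-validation techniques for evaluating predictive performance". For the 6-week change, section 10.4.2 will "conduct two regression analyses: (1) using power Doppler measurements and (2) using LEAD ultrasound measurements". It then adds models for each single time point (baseline, 3 weeks, 6 weeks), "separately for each imaging modality using a similar approach as outlined above".

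**Patients.** The primary analysis aims for 20 complete arm 1 patients (section 10.3.1). The secondary set is wider: "All patients who have completed at least one LEAD and Doppler ultrasound exam at any time point" (section 10.4.1). The models therefore share most patients, but not necessarily all.

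**Selection and next step.** Under section 10.7, "the predictive model that yields the best AUC will be selected for future studies". The trigger for the follow-up is "If any predictive model from this pilot study has an AUC of at least 0.7". Random forests or CART may be added if models perform equally well. The follow-up's sample size and operating characteristics "will be determined based on findings from this pilot study and other data available". Its purpose, in an independent cohort, is to "validate the predictive model and determine its AUC with a smaller margin of error". A randomized trial comes after that.

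No section asks for the selected model's AUC to be corrected for having been selected.

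**The concern.** Each pilot AUC is a noisy estimate. The highest of nine tends to be the one that chance favoured most, so on average it overstates what that model will do in new patients. Cross-validation as described deals with a different problem, the optimism from fitting one model and scoring it on the same patients. Nine honestly cross-validated AUCs still have an optimistic maximum.

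What is at stake is planning. Section 10.7 lets pilot findings inform the size and operating characteristics of the follow-up, and independent validation can reveal the optimism only after that study has been sized.

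**Working it through.** **Count of models.** LEAD 3-week change: 1. The 6-week change by modality: 2. Three time points for each of two modalities: 3 × 2 = 6. Total 1 + 2 + 6 = 9, more if random forests or CART are added.

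**Noise in one AUC.** Inputs from section 10.5: 20 patients, 59% responders (0.59 × 20 = 11.8, so 12 and 8), true AUC 0.7, stated margin 0.14. The Hanley-McNeil standard error is

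SE² = [A(1−A) + (n₁−1)(Q₁−A²) + (n₀−1)(Q₂−A²)] / (n₁n₀), with Q₁ = A/(2−A) and Q₂ = 2A²/(1+A).

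With A = 0.7, n₁ = 12, n₀ = 8: Q₁ = 0.538, Q₂ = 0.576, SE² = (0.210 + 0.533 + 0.605)/96 = 0.0140, SE = 0.118. The 95% margin is 1.96 × 0.118 = 0.23. The stated 0.14 does not reproduce as a 95% margin; it corresponds to about 76% confidence. That is a separate matter. Here it shows only that each AUC is noisy enough for the choice of the maximum to count.

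**Bias from taking the maximum.** Simulation: nine binormal scores, 12 against 8 patients, common between-model correlation of 0.5 or 0.8 (assumed, as the protocol gives none). Raw bias is the mean best AUC minus the true AUC of the chosen model. The corrected AUC repeats the choice inside stratified 4-fold cross-validation; its bias is taken over all simulated pilots.

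| True AUCs | Raw bias, correlation 0.5 / 0.8 | Bias of corrected AUC, 0.5 / 0.8 |
|---|---|---|
| All 0.5 | 0.146 / 0.117 (second value at 0.7) | +0.002 / +0.002 |
| All 0.7 | 0.128 / 0.086 | 0.000 / −0.001 |
| One 0.7, eight 0.6 | 0.125 / 0.069 | −0.005 / −0.014 |
| One 0.8, eight 0.65 | 0.089 / 0.032 | −0.011 / −0.016 |
| One 0.8, eight 0.6 | 0.064 / 0.013 | −0.017 / −0.016 |
| One 0.8, eight 0.5 | 0.020 / 0.000 | −0.018 / −0.004 |

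With one model at 0.7 and eight at 0.5 the raw bias is 0.078 / 0.017. Overall the raw bias is about 0.00 to 0.15, and repeat runs put the corrected AUC within about 0.03 of the truth.

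**With Lasso refitted.** A smaller simulation (300 trials per setting, three parameters per model, fixed penalty) points the same way. Raw bias ran from 0.803 − 0.747 = 0.056 to 0.716 − 0.500 = 0.216. The corrected AUC was within about 0.04, mostly on the low side.

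**Only pilots that pass the go rule have a follow-up to plan.** Because the 0.7 rule acts on the raw AUC, passing it is itself a selection. Among passing pilots the raw AUC was 0.03 to 0.27 too high and the corrected AUC still about 0.00 to 0.18 too high. Root mean squared error there was 0.08 to 0.28 raw and 0.08 to 0.20 corrected, similar or smaller in each setting.

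**Effect on follow-up size.** This depends on a target that section 10.7 does not give. Using the same SE with 59% responders:

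| Planning AUC | 95% margin of 0.10 (assumed target) | 90% chance of observing at least 0.7 (assumed target) |
|---|---|---|
| 0.79 | 76 | 41 |
| 0.77 | 83 | 73 |
| 0.75 | 89 | 151 |

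Under the precision target the size rises by 89/76 − 1 = 17%. Under the other it more than triples.

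**The case against.** **This is detail for an SAP.** How folds are built may well be. But the selection rule, the go rule and the basis for planning are all fixed in section 10.7, and no passage calls for correcting the winner's AUC. Nested cross-validation is compatible with section 10.3.2, but it is not stated. The point stands.

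**The study is exploratory and the optimism will be caught.** Largely right, and it limits the severity. The protocol disclaims formal testing, calls its secondary endpoints hypothesis-generating, and requires an independent cohort and then a randomized trial.

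**The raw AUC need not size the follow-up.** Also right. A reader might infer that section 10.7 plans the follow-up on the raw best AUC and will therefore undersize it. The text does not say so. It refers to pilot findings and other data, and section 10.3.2 provides a 95% confidence interval. The stated aim of a smaller margin of error also suits a precision target, under which size changes modestly.

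**The correction is not a cure.** Correct: it is close to unbiased over all pilots, but not among those that go forward.

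**Conclusion.** The selected model's AUC will be biased upward under the stated rule, by about 0.00 to 0.15. This rests on 12 responders and 8 non-responders, nine models, binormal scores and between-model correlation of 0.5 to 0.8. The bias approaches zero only when one model clearly dominates. Neither the correlation nor the spread of true AUCs is known.

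A reader might also infer that the go rule is unsound. If all nine true AUCs were 0.5, at least one would reach 0.7 in 13% to 47% of pilots (correlation 0.95 to 0), against about 7% for a single model. The documents do not make this an error. A lenient gate before independent validation is a legitimate choice, as are the search over modalities and time points and the decision not to adjust exploratory tests.

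Severity is moderate to low: a planning figure is inflated, and no patient-care decision rests on it.

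**What to change.** Keep the search and the 0.7 go rule. Add to section 10.7: *The AUC of the selected model will be reported together with a selection-corrected AUC, obtained by repeating the choice among all fitted models, including any random forest or CART models, inside each cross-validation fold. Planning of the follow-up study will use the corrected AUC with its uncertainty, not the raw best AUC, and will consider a range of AUCs below it.* The last clause is needed because the corrected figure stays optimistic among pilots that pass the go rule. Whether to apply the 0.7 gate to the corrected AUC is a trade-off for the sponsor.

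Costs:
- Two sentences and some computation on data already planned; no new patients or exams, and the go rate is unchanged.
- Slight pessimism, because each fold chooses on fewer patients.
- Extra noise if one model is clearly best (root mean squared error 0.13 against 0.11 with one model at 0.8, eight at 0.5 and correlation 0.5).
- Possibly a larger follow-up.
- A stated rule for patients who lack an exam that some of the models need.
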